10.1.10 Publication policy

- The results of this study may be published or presented at scientific meetings. If this is foreseen, the Investigator agrees to submit all manuscripts or abstracts to the Sponsor before submission. This allows the Sponsor to protect proprietary information and to provide comments.
- The Sponsor will comply with the requirements for publication of study results. In accordance with standard editorial and ethical practice, the Sponsor will generally support publication of multicenter studies only in their entirety and not as individual site data. In this case, a coordinating Investigator will be designated by mutual agreement.
- Authorship will be determined by mutual agreement and in line with International Committee of Medical Journal Editors authorship requirements.

10.2 APPENDIX 2: CLINICAL LABORATORY TESTS

The tests detailed in [Table 11](#) will be performed by the central or local laboratory (as mentioned in the table).

Additional tests may be performed at any time during the study as determined necessary by the Investigator or required by local regulations.

Table 11 - Protocol-required laboratory assessments

Laboratory assessments	Parameters			
Hematology (central)	Platelet count	RBC indices:	White blood cell (WBC) count with differential:	
	Red blood cell (RBC) count	MCV	Neutrophils	
	Hemoglobin	MCH	Lymphocytes	
	Hematocrit	% reticulocytes	Monocytes	
			Eosinophils	
			Basophils	
Clinical chemistry (central) ^a	Blood urea nitrogen (BUN)	Potassium	Aspartate aminotransferase (AST)/ serum glutamic-oxaloacetic transaminase (SGOT)	Total and direct bilirubin
	Creatinine	Sodium	Alanine aminotransferase (ALT)/ serum glutamic-pyruvic transaminase (SGPT)	Total protein
	Glucose	Calcium	Alkaline phosphatase	Serum FSH Serum human chorionic gonadotropin (HCG) pregnancy test
	Creatine phosphokinase (CPK) ^b			
Routine urinalysis (central)	
 • Specific gravity • pH, glucose, protein, blood, ketones, bilirubin, urobilinogen, nitrite, leukocyte esterase by dipstick • Microscopic examination (if blood or protein) 			
Other screening tests (local)	
 • Urine human chorionic gonadotropin (HCG) pregnancy test (as needed for women of childbearing potential)^c 			
The results of each locally done test must be entered into the eCRF.				

NOTES:

a Details of liver chemistry stopping criteria and required actions and follow-up assessments after observations of ALT $>3 \times$ ULN are given in Appendix 6, [Section 10.6](#). Clinical laboratory findings of ALT $\geq 3 \times$ upper limit of normal (ULN) and bilirubin $\geq 2 \times$ ULN ($>35\%$ direct bilirubin) or ALT $\geq 3 \times$ ULN and international normalized ratio (INR) >1.5 , if INR measured that may suggest severe liver injury must be reported as an SAE.

b Required in Year 1 only

c Local urine testing is sufficient unless a pregnancy is detected or the urine test is inconclusive and a serum test needs to be used for verification, or only serum testing is required by local regulation or IRB/IEC.

Investigators must document their review of each laboratory safety report.

10.3 APPENDIX 3: ADVERSE EVENTS: DEFINITIONS AND PROCEDURES FOR RECORDING, EVALUATING, FOLLOW-UP, AND REPORTING

DEFINITION OF AE

AE definition

- An AE is any untoward medical occurrence in a patient or clinical study participant, temporally associated with the use of study intervention, whether or not considered related to the study intervention.
- NOTE: An AE can therefore be any unfavorable and unintended sign (including an abnormal laboratory finding), symptom, or disease (new or exacerbated) temporally associated with the use of study intervention.

Events meeting the AE definition

- Any abnormal laboratory test results (hematology, clinical chemistry, or urinalysis) or other safety assessments (eg, ECG, radiological scans, vital signs measurements), including those that worsen from baseline, considered clinically significant in the medical and scientific judgment of the Investigator (ie, not related to progression of underlying disease),
- Exacerbation of a chronic or intermittent pre-existing condition including either an increase in frequency and/or intensity of the condition.
- New conditions detected or diagnosed after study intervention administration even though it may have been present before the start of the study.
- Signs, symptoms, or the clinical sequelae of a suspected drug-drug interaction.
- Signs, symptoms, or the clinical sequelae of a suspected overdose of either study intervention or a concomitant medication.
- "Lack of efficacy" or "failure of expected pharmacological action" per se will not be reported as an AE or SAE. Such instances will be captured in the efficacy assessments. However, the signs, symptoms, and/or clinical sequelae resulting from lack of efficacy will be reported as AE or SAE if they fulfil the definition of an AE or SAE.
- The signs, symptoms, and/or clinical sequelae resulting from lack of efficacy will be reported as AE or SAE if they fulfil the definition of an AE or SAE. Also, "lack of efficacy" or "failure of expected pharmacological action" also constitutes an AE or SAE.

Events NOT meeting the AE definition

- Any clinically significant abnormal laboratory findings or other abnormal safety assessments which are associated with the underlying disease, unless judged by the Investigator to be more severe than expected for the participant's condition.
- The disease/disorder being studied or expected progression, signs, or symptoms of the disease/disorder being studied, unless more severe than expected for the participant's condition.

- Medical or surgical procedure (eg, endoscopy, appendectomy): the condition that leads to the procedure is the AE.
- Situations in which an untoward medical occurrence did not occur (social and/or convenience admission to a hospital).
- Anticipated day-to-day fluctuations of pre-existing disease(s) or condition(s) present or detected at the start of the study that do not worsen.

DEFINITION OF SAE

If an event is not an AE per definition above, then it cannot be an SAE even if serious conditions are met (eg, hospitalization for signs/symptoms of the disease under study, death due to progression of disease).

A SAE is defined as any untoward medical occurrence that, at any dose:

a) Results in death

b) Is life-threatening

The term “life-threatening” in the definition of “serious” refers to an event in which the participant was at risk of death at the time of the event. It does not refer to an event, which hypothetically might have caused death, if it were more severe.

c) Requires inpatient hospitalization or prolongation of existing hospitalization

In general, hospitalization signifies that the participant has been detained (usually involving at least an overnight stay) at the hospital or emergency ward for observation and/or treatment that would not have been appropriate in the physician’s office or outpatient setting. Complications that occur during hospitalization are AEs. If a complication prolongs hospitalization or fulfills any other serious criteria, the event is serious. When in doubt as to whether “hospitalization” occurred or was necessary, the AE should be considered serious.

Hospitalization for elective treatment of a pre-existing condition that did not worsen from baseline is not considered an AE.

d) Results in persistent disability/incapacity

- The term disability means a substantial disruption of a person’s ability to conduct normal life functions.
- This definition is not intended to include experiences of relatively minor medical significance such as uncomplicated headache, nausea, vomiting, diarrhea, influenza, and accidental trauma (eg, sprained ankle) which may interfere with or prevent everyday life functions but do not constitute a substantial disruption.

e) Is a congenital anomaly/birth defect

f) Other situations:

- Medical or scientific judgment should be exercised in deciding whether SAE reporting is appropriate in other situations such as important medical events that may not be immediately life-threatening or result in death or hospitalization but may jeopardize the participant or may require medical or surgical intervention to prevent one of the other outcomes listed in the above definition. These events should usually be considered serious.
- Examples of such events include invasive or malignant cancers, intensive treatment in an emergency room or at home for allergic bronchospasm, blood dyscrasias or convulsions that do not result in hospitalization, or development of drug dependency or drug abuse.

RECORDING AND FOLLOW-UP OF AE AND/OR SAE

AE and SAE recording

- When an AE/SAE occurs, it is the responsibility of the Investigator to review all documentation (eg, hospital progress notes, laboratory reports, and diagnostics reports) related to the event.
- The Investigator will then record all relevant AE/SAE information in the CRF.
- It is **not** acceptable for the Investigator to send photocopies of the participant's medical records to the Sponsor's representative in lieu of completion of the AE/SAE CRF page.
- There may be instances when copies of medical records for certain cases are requested by the Sponsor's representative. In this case, all participant identifiers, with the exception of the participant number, will be redacted on the copies of the medical records before submission to the Sponsor's representative.
- The Investigator will attempt to establish a diagnosis of the event based on signs, symptoms, and/or other clinical information. Whenever possible, the diagnosis (not the individual signs/symptoms) will be documented as the AE/SAE.

Assessment of intensity

The Investigator will make an assessment of intensity for each AE and SAE reported during the study and assign it to 1 of the following categories:

- Mild: An event that is easily tolerated by the participant, causing minimal discomfort and not interfering with everyday activities.
- Moderate: An event that causes sufficient discomfort and interferes with normal everyday activities.
- Severe: An event that prevents normal everyday activities. An AE that is assessed as severe should not be confused with a SAE. Severe is a category utilized for rating the intensity of an event; and both AEs and SAEs can be assessed as severe.

An event is defined as “serious” when it meets at least 1 of the predefined outcomes as described in the definition of an SAE, NOT when it is rated as severe.

Assessment of causality

- The Investigator is obligated to assess the relationship between study intervention and each occurrence of each AE/SAE.
- A "reasonable possibility" of a relationship conveys that there are facts, evidence, and/or arguments to suggest a causal relationship, rather than a relationship cannot be ruled out.
- The Investigator will use clinical judgment to determine the relationship.
- Alternative causes, such as underlying disease(s), concomitant therapy, and other risk factors, as well as the temporal relationship of the event to study intervention administration will be considered and investigated.
- The Investigator will also consult the IB and/or Product Information, for marketed products, in his/her assessment.
- For each AE/SAE, the Investigator **must** document in the medical notes that he/she has reviewed the AE/SAE and has provided an assessment of causality.
- There may be situations in which an SAE has occurred, and the Investigator has minimal information to include in the initial report to the Sponsor’s representative. However, **it is very important that the Investigator always make an assessment of causality for every event before the initial transmission of the SAE data to the Sponsor’s representative.**
- The Investigator may change his/her opinion of causality in light of follow-up information and send an SAE follow-up report with the updated causality assessment.
- The causality assessment is one of the criteria used when determining regulatory reporting requirements.

Follow-up of AEs and SAEs

- The Investigator is obligated to perform or arrange for the conduct of supplemental measurements and/or evaluations as medically indicated or as requested by the Sponsor’s representative to elucidate the nature and/or causality of the AE or SAE as fully as possible. This may include additional laboratory tests or investigations, histopathological examinations, or consultation with other health care professionals.
- If a participant dies during participation in the study or during a recognized follow-up period, the Investigator will provide Sponsor’s representative with a copy of any post-mortem findings including histopathology.
- New or updated information will be recorded in the originally completed CRF.
- The Investigator will submit any updated SAE data to the Sponsor within 24 hours of receipt of the information.

REPORTING OF SAES

SAE reporting to the Sponsor's representative via an electronic data collection tool

- The primary mechanism for reporting an SAE to the Sponsor's representative will be the electronic data collection tool.
- If the electronic system is unavailable, then the site will use the paper SAE data collection tool (see next section) in order to report the event within 24 hours.
- The site will enter the SAE data into the electronic system as soon as it becomes available.
- After the study is completed at a given site, the electronic data collection tool will be taken off-line to prevent the entry of new data or changes to existing data.
- If a site receives a report of a new SAE from a study participant or receives updated data on a previously reported SAE after the electronic data collection tool has been taken off-line, then the site can report this information on a paper SAE form (see next section) or to the Sponsor's representative by telephone.
- Contacts for SAE reporting can be found in the study manual.

SAE reporting to the Sponsor's representative via paper CRF

- Facsimile transmission of the SAE paper CRF is the preferred method to transmit this information to the Sponsor's representative.
- In rare circumstances and in the absence of facsimile equipment, notification by telephone is acceptable with a copy of the SAE data collection tool sent by overnight mail or courier service.
- Initial notification via telephone does not replace the need for the Investigator to complete and sign the SAE CRF pages within the designated reporting time frames.
- Contacts for SAE reporting can be found in the study manual.

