8.1.2 MS Relapse

8.1.2.1 Unscheduled assessment visits for a suspected MS relapse

Participants must be instructed to immediately report new neurological symptoms and recurring or worsening of previous symptoms to the Investigator. Any reported symptoms will be collected. If a participant reports symptoms that may be consistent with relapse, an unscheduled assessment visit with the Investigator will be scheduled as soon as possible (whenever possible within 7 days of onset of symptoms). The Investigator will assess whether the reported episode is consistent with the definition of MS relapse (see [Section 8.1.2.2](#)). If it is consistent with the definition of MS relapse or if there is any doubt and relapse cannot be ruled out, an EDSS assessment should be performed and PK and [REDACTED] samples will be collected.

All MS relapses are to be reported on the MS relapse eCRF page. Multiple sclerosis relapse should not be reported as an AE/SAE unless, in the judgment of the Investigator, it is unusually severe or medically unexpected (see [Section 8.3.6](#) for reporting rules).

Unscheduled visits as detailed in the SoA ([Section 1.3](#)) must be categorized as being related to MS (or not), and additional examinations or laboratory tests are needed for safety follow up and optimal treatment decisions.

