8.2 SAFETY ASSESSMENTS

Planned time points for all safety assessments are provided in the SoA ([Section 1.3](#)).

The definitions of AEs and SAEs can be found in Appendix 3 ([Section 10.3](#)). For the purpose of this protocol, MS relapses ([Section 8.1.2](#)) are waived from reporting as AEs except if they meet the criteria of an SAE. Nonserious MS relapses will be collected on a special eCRF page and will be analyzed as an efficacy endpoint. Following an MS relapse assessment, ([Section 8.1.2](#)), events that are concluded as not meeting the criteria of an MS relapse will be reported as AEs.

The last EDSS and MRI obtained in the DRI15928 study are acceptable if they are performed within 6 weeks prior to Day 1 of the LTS16004 study.

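### Appendix 3 says both that lack of efficacy is not and that it is an AE or SAE, and the protocol gives two different sole exceptions for reporting an MS relapse as an AE or SAE

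*Protocol*

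**What the plan says.** **Lack of efficacy.** In Protocol Appendix 3 (Section 10.3), the list of events meeting the AE definition has two adjacent bullets. The first says that lack of efficacy "per se will not be reported as an AE or SAE" and sends such cases to the efficacy assessments. The second says that it "also constitutes an AE or SAE".

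**Relapse, first rule.** Section 8.1.2.1: "Multiple sclerosis relapse should not be reported as an AE/SAE unless, in the judgment of the Investigator, it is unusually severe or medically unexpected". SAP 2.1.4 repeats this exception and no other. Section 8.1.2.1 refers the reader to Section 8.3.6 for reporting rules.

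**Relapse, second rule.** Section 8.2 says that relapses "are waived from reporting as AEs except if they meet the criteria of an SAE", and that nonserious relapses go to a special eCRF page for analysis as efficacy. Section 8.3.9 restates the SAE exception, applies the exemption to efficacy endpoints generally, and removes routine hospitalization for relapse as a seriousness criterion.

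**Definitions that bear on both.** Appendix 3 separates intensity from seriousness: "An AE that is assessed as severe should not be confused with a SAE". Its list of events that are not AEs includes "symptoms of the disease/disorder being studied, unless more severe than expected" for the participant's condition. Its SAE definition opens with an ordering rule: "If an event is not an AE per definition above, then it cannot be an SAE even if serious conditions are met". Its final seriousness item, (f), lets medical judgment make an important medical event serious.

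**The concern.** The two lack-of-efficacy bullets give opposite instructions. The second also sits poorly with the exemption of efficacy endpoints in Section 8.3.9.

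The relapse rules use different tests. One turns on severity or unexpectedness, the other on seriousness, and each is worded as the only exception. Sites following different sections could enter the same relapse as an AE at one centre and only on the relapse page at another.

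AEs and SAEs are the primary endpoint (Protocol Section 3). The overview in SAP 2.4.5.1 counts participants with any TEAE, any treatment-emergent SAE and any severe TEAE. An unusually severe relapse is a natural candidate for the severe row, so the contents of these rows would depend partly on which section was read. If serious relapses are also treated differently, the 24-hour reporting duty for SAEs in Section 8.3.3 differs with them.

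**Working it through.** The plan states no figure on this point, so the check is a comparison of texts, followed by simple arithmetic for scale.

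**Step 1: apply both relapse rules to four cases.**

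| Relapse | 8.1.2.1 and SAP 2.1.4 | 8.2 and 8.3.9 |
|---|---|---|
| Serious; unusually severe or unexpected | reported | reported |
| Nonserious; neither severe beyond the usual nor unexpected | not reported | not reported |
| Nonserious; unusually severe or unexpected | reported | waived, relapse page only |
| Serious; expected severity, not unexpected | not reported | reported on the face of the text |

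The rules part in the last two rows.

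**Step 2: see whether other text closes the gap.**

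- *Third row.* Item (f) of the SAE definition may make some of these relapses serious, and those are then reported under both rules. Relapses that stay nonserious after item (f) remain divided.
- *Fourth row.* Section 8.2 refers to Appendix 3 for the AE and SAE definitions. Read in that order, a relapse of expected severity is not an AE and so cannot be an SAE, and both rules exempt it. Without that reading, the row stays divided.
- *Cross-reference.* Section 8.3.6 covers regulatory reporting of SAEs and has no relapse rule; the relapse rule is in 8.3.9. The pointer in 8.1.2.1 does not settle the matter.

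**Step 3: see what the SAP outputs can show.** The tables by preferred term and the SAE listing (SAP 2.4.5.1) identify relapses that were entered as AEs or SAEs. They cannot show relapses that a site left off the AE page. The annualized relapse rate does not depend on the choice: "All MS relapses are to be reported on the MS relapse eCRF page", and SAP 2.4.4 counts confirmed relapses with onset on treatment.

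**Step 4: scale.** A disputed relapse moves an overview row only if it is that participant's only event in the row.

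- Overall: 126 enrolled (SAP 1.3). 1/126 = 0.79 percentage points, taking all 126 as treated, because the AE denominator is the safety population.
- By dose group: Protocol Section 6.3 describes eight arms, four doses in each of two cohorts, at equal ratio. 130/8 = 16.25, so arms of 16 or 17, and 32 to 34 participants per dose.
- Not enrolled: 130 − 126 = 4. If these fall in any pattern, the smallest group is 32 − 4 = 28 and the largest is 34.
- 1/34 = 2.94 and 1/28 = 3.57 percentage points. At an even split, 126/4 = 31.5 and 1/31.5 = 3.17.

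**The case against.** **The relapse rules need not collide.** Waiving or exempting relapses lifts a duty to report and need not forbid reporting. Read permissively, Sections 8.2 and 8.3.9 allow a site to report an unusually severe nonserious relapse, and 8.1.2.1 can stand beside them. A reader might infer that the rules conflict on any reading. The documents do not support that, because of this permissive reading and because item (f) narrows the disputed case. What remains is that, on the permissive reading, reporting is left to the site, which still makes the counts depend on local choice.

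**The serious case may dissolve.** Under the AE-before-SAE order, a serious relapse of expected severity is exempt under both rules. One could reply that the routine-hospitalization provision in 8.3.9 then has little left to do, but it would still apply to a relapse that is more severe than expected and routinely admitted. This case is therefore possible, not certain.

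**The lack-of-efficacy bullet looks like an editing leftover.** It opens by repeating the last sentence of the bullet before it, which suggests that two alternative texts were both kept. That explains the contradiction but does not remove it. A reader might also see a direct conflict with Section 8.3.10 on MS findings on MRI. That link is only indirect, since no passage defines such findings as lack of efficacy.

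**The impact is contained.** Relapse information is kept on its own page, the relapse rate is safe, and SAP 2.4 plans no p-values. All of this stands. It limits the consequence to the reported incidences, which are the primary endpoint.

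**Conclusion.** The point holds as a contradiction in Appendix 3 and as two unreconciled relapse-reporting rules. It should be fixed. The firm part of the relapse issue is the relapse that is unusually severe or unexpected and remains nonserious: it is reportable under 8.1.2.1 and SAP 2.1.4, and waived, or at best left to the site, under 8.2 and 8.3.9. TEAE and severe-TEAE counts are exposed; SAE counts are exposed only if Sections 8.2 and 8.3.9 are not read through Appendix 3.

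The size is unknown, because the documents give no number of affected relapses. The shifts of about 0.8 points overall and 2.9 to 3.6 points in a dose group are what one participant contributes to a row in a study this small. They are not an estimate of effect. They assume that all enrolled participants were treated, equal allocation over the eight arms, and any spread of the four not enrolled.

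A reader might infer from Protocol Section 2.3, where the one treatment-emergent SAE reported from DRI15928 was an MS relapse (1/130 = 0.8%), that the ambiguity has already changed counts. The documents do not support this: they do not say under which rule that event was reported. It shows only that relapses can appear among the SAEs.

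**What to change.** 1. Remove the second lack-of-efficacy statement in Appendix 3.
2. Reconcile Protocol Sections 8.1.2.1, 8.2 and 8.3.9 and SAP 2.1.4 to one relapse-reporting criterion of the sponsor's choice, consistent with the AE-before-SAE order in Appendix 3. State whether the exemption forbids reporting or only lifts the duty.
3. Correct the cross-reference in Section 8.1.2.1 to include Section 8.3.9.
4. Text edits cannot repair records already filed under different rules, and SAP 1.6 expects the study to end in 2024. So add a listing that matches each relapse eCRF record to any AE or SAE record, and show the TEAE and SAE overview with and without MS-relapse terms.

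The cost is text edits and a small amount of extra programming on data already collected.
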